Frailty is defined as a decreased resistance to disability and illness. It is common (as high as 17% in advance lung disease) and associated with important patient outcomes of mortality, hospitalization, and need for nursing home.(1, 2) Frailty consists of a constellation of three or more of the following characteristics: wasting, exhaustion, decreased physical activity, slowness, and weakness.(3) Patient’s with one or more characteristics are considered “pre-frail” and those with three or more are considered “frail.” Wasting is defined as unexplained weight loss or decrease in lean body mass. It is typically measured by body composition. Exhaustion is typically measured by self-report via questionnaire. Physical activity can be self-reported through questionnaires or, more accurately, directly measured by physical activity monitors. Slowness is typically measured by gait speed (the time it takes an individual to walk 15 feet). Finally, weakness can be measured by respiratory muscle function or hand grip strength. Measures are typically adjusted for sex and height or weight and compared to expected normative values.

Little is known about frailty in patients with chronic lung disease. Emerging evidence suggests that frailty is important for both mortality and disease-specific outcomes in lung disease patients. Evidence demonstrates the above-referenced frailty characteristics are common in chronic obstructive pulmonary disease (COPD). For example, patients with COPD have been noted in separate studies to have wasting(8, 9), fatigue(10), lower physical activity(11), slower gait speed(12), or decreased strength (13). In addition, wasting has been associated with COPD mortality, and increased fatigue has been associated with increased COPD hospitalizations.(8, 10). These studies suggest the possible importance of the frailty phenotype in COPD. In addition, a mixed measure of frailty with functional and sensory deficits that found the mixed measure is associated with increased shortness of breath, health care utilization and disabilities in COPD.(15) A similar constellation of deficits was associated with an increased mortality at 12 years in patients with COPD.(16) Finally, this candidate has demonstrated that frailty is associated with increased mortality and hospitalization in COPD. (see

“Does pulmonary rehabilitation improve frailty in chronic lung disease?”

Principal Investigator (Last, First Middle): [name]

Updated: 6/23/2015

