preliminary data) Less is known about other chronic lung diseases and frailty. However, this candidate demonstrated that low muscle index (wasting) pretransplant is associated with worse survival and increased primary graft dysfunction following lung transplantation. (see preliminary data) Lung transplant candidates are typically a mixed representation of several chronic lung diseases, therefore, suggesting importance of frailty beyond COPD.

In the above mentioned preliminary data, research participants underwent pulmonary rehabilitation. Despite this frailty and frailty characteristics persisted. This suggests that pulmonary rehabilitation alone may be *insufficient* to address frailty in its current form. Prior studies have attempted to identify patient factors that lead to success in pulmonary rehabilitation. (14) It is unknown if such factors will be important to successful improvement in frailty characteristics.

Proposed methodology

We propose a single-center, prospective cohort study with **Aim 1**: measurements of frailty characteristics pre- and post-pulmonary rehabilitation referral and **Aim 2**: measurements of baseline affect, uncertainty, and demographics to examine associations between patient characteristics and improvements in frailty characteristics.

Outcomes

Aim 1: Outcomes will include median change in grip strength, gait speed, physical activity, and body composition and comparison of pre and post self-reported exhaustion. In addition, prevalence of frailty and pre-frailty will be compared pre and post pulmonary rehabilitation. **Aim 2**: Associations of positive or negative affect, baseline measure of uncertainty, and demographic factors and median or percent change in frailty characteristics.

Summary of background and significance:

Frailty is common in advanced lung disease and is associated with decreased time to hospitalization, increased length of hospital stay, and increased mortality. In addition, in lung transplant patients frailty is associated with increased primary graft dysfunction and mortality. There is a knowledge gap regarding effective interventions to treat frailty and frailty characteristics. Pulmonary rehabilitation is widely available and utilized in patients with moderate to severe lung disease. Whether pulmonary rehabilitation improves frailty is unknown.

Alignment with career goals:

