Participants and Criteria: Patients will be identified from the Mayo Clinic Rochester, MN Pulmonary Division. Patients who either are referred to enroll in pulmonary rehabilitation at Mayo Clinic in Rochester or who are referred for nursing education regarding pulmonary rehabilitation enrollment will be approached. **Recruitment:** A study referral reminder will be incorporated into the pulmonary rehabilitation referral and pulmonary rehabilitation nursing education referrals. **Inclusion/Exclusion criteria:** Eligible patients will be aged 18 years or older, referred for pulmonary rehabilitation, and consenting to research. **Retention strategy:** Patients will be given remuneration for completing the 3 to 6 month follow-up appointment. **Methods:** This is a single-center, prospective trial examining the effects of pulmonary rehabilitation on frailty and frailty characteristics and associations between patient characteristics and improvement in frailty characteristics. Patient will be approached for recruitment in a private setting regarding willingness to participate in the study by the principal investigator or other authorized study personnel and consented with IRB-approved consent procedure and written consent form. Patients will receive a full explanation of all procedures, risks, benefits, and alternatives and all questions will be answered. Once consented patient will undergo physiologic testing and complete questionnaires. Activity monitors will be sent with patients (including a return addressed envelope with postage) to assess one week of measured activity. At three to six months physiologic testing and activity monitor recordings will be repeated. Patients will also be asked to specify the number of completed pulmonary rehabilitation sessions. **Data: Medical Record Abstraction** Patient demographics, pulmonary diagnoses, weight, height, and pulmonary function tests will be recorded. **Physiologic Measurements and Testing: Grip strength** will be measured using a Jamar Digital Hand Held Dynamometer. Three serial measurements will be taken (using the dominant hand), averaged, and adjusted by gender and BMI using normative table. **Gait Speed** will be measured using a wireless infrared timing system. Self-selected walking speed over a distance of 15 feet will be averaged over 3 trials and then adjusted for gender and height. **Dual Energy X-ray Absorptiometry (DEXA) scan** will determine body composition (body mass, fat mass and fat-free mass) at baseline and at 3-6 months following initiation of pulmonary rehabilitation. **State-of-the-art activity monitors (Sensewear Armband, Body media, Pittsburgh,PA)** will quantify kcals burned, active and sleep time, as well as quality of sleep (baseline and 3 to 6 months following initiation of pulmonary rehabilitation).

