
Questionnaires

Name of questionnaire	abbrev	Purpose of questionnaire	N of items	Cronbach's alpha
Mischel Uncertainty in Illness Scale	MUIS	Uncertainty in illness measure	33	0.65-0.90
Positive Affect Negative Affect Schedule	PANAS	Positive and negative affect	20	0.84-0.90
Chronic Respiratory Questionnaire	CRQ	Disease-specific quality of life measure in lung disease	20	0.84
Short form Health Survey-26	SF-36	Exhaustion question only	1	0.82-0.95

Sample size A convenience sample of consecutive prospective consenting patients will be enrolled. This is a pilot study and therefore sample size calculations are not required. However, in order to inform our enrollment we have made the following calculations: **Change in grip strength.** A sample size of 40 per sample will have 80% power to detect a difference in means of 20%, assuming a baseline mean of 28 in women and a standard deviation of 6.3 (as reported for females age range 50-59), using a paired t-test with a 0.05 two-sided significance level.(17) However, given an estimated prevalence of frailty of 17% we would like to recruit at least 100 patients to further study frailty in a larger sample. Based on annual pulmonary rehabilitation participants at Mayo Clinic in Rochester (~150 patients), annual referrals for nursing pulmonary education (~250-300 patients), and a recruitment rate of 80% for similar studies, we feel this is realistic.

Quality Assurance / Quality Controls:

Data abstraction Spreadsheet will be standardized (for definitions and protocol) and audited by PI weekly to ensure selection criteria and protocol compliance and monthly for completion and accuracy.

Personnel training All personnel will be trained to perform the hand grip and gait speed assessments.

Analysis plan:

Patient demographic characteristics will be summarized by mean, median and standard deviation and range (continuous variables) and counts and percents (categorical variables). A two-tailed p < 0.05 will be considered statistically significant. Frail performance will be defined as a performance of <20% predicted on physiologic tests. Pre- and post- intervention

tests will be compared using Wilcoxon Signed Rank or paired t-test as appropriate. Subgroup analysis will be performed for frail patients and those completing > 6 and > 12 pulmonary rehabilitation sessions.

Budget

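### Neither one-week activity recording is kept clear of rehabilitation sessions, so supervised exercise may be counted in the Aim 1 activity change and the planned data would not show it

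*Combined protocol and SAP*

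**What the plan says.** Specific Aim #1, Methods, sets the baseline recording after consent: "Activity monitors will be sent with patients (including a return addressed envelope with postage) to assess one week of measured activity". For follow-up it says: "At three to six months physiologic testing and activity monitor recordings will be repeated". That sentence does not say from what date the months are counted. Later in the same section, the description of the armband says that it "will quantify kcals burned, active and sleep time, as well as quality of sleep (baseline and 3 to 6 months following initiation of pulmonary rehabilitation", which counts from the start of rehabilitation. No sentence counts from its completion.

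The session information is one item: "Patients will also be asked to specify the number of completed pulmonary rehabilitation sessions". The list of data to be abstracted from the medical record does not include session dates. Those approached include patients "who are referred for nursing education regarding pulmonary rehabilitation enrollment will be approached", as well as those referred to enrol at the centre.

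Activity is a named result. In the Outcomes section, under Aim 1: "Outcomes will include median change in grip strength, gait speed, physical activity, and body composition". Background and significance prefers monitors for this item: "Physical activity can be self-reported through questionnaires or, more accurately, directly measured by physical activity monitors". Low activity is also one of the five characteristics that define frailty and pre-frailty, whose prevalence is compared before and after rehabilitation. The Analysis plan compares the two occasions by Wilcoxon signed rank or paired t-test, with no step for days or hours spent in sessions.

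**The concern.** Aim 1 asks whether rehabilitation changes a characteristic of the patient. If the armband is worn during supervised exercise, part of what it records is the intervention itself. A patient still attending when the second monitor goes home would show more calories and active time even if nothing outside the sessions had changed. A patient whose first sessions fall in the baseline week would show the reverse, and a real gain could be hidden. There is no comparison group to offset either effect, and the same reading may feed into the frailty and pre-frailty prevalences. With only a total session count, nobody could establish afterwards how many recordings were affected.

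**Working it through.** The plan gives no figure on this point, so there is none to reproduce. The check has four steps; every input marked assumed is absent from the documents.

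**1. When can overlap occur?** Let D be the weeks from enrolment to the first session, L the weeks from first to last session, and T the week of the follow-up recording. Three to six months is about 13 to 26 weeks.

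- Counted from the start of rehabilitation: the follow-up week can contain sessions only if L is at least T, so at least about 13 weeks.
- Counted from enrolment: the condition is D + L at least T, so D + L at least about 13 weeks.
- Baseline, if the monitor is worn straight after enrolment: overlap needs D below about one week.

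The documents give neither D nor L. The overlapping share f is therefore unknown, between 0 and 100%. For a patient who never starts, an interval counted from the start has no date at all, which is a further reason to reconcile the two statements.

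**2. How large is it in an overlapping patient?** Added minutes per day = sessions per week × active minutes per session / 7. Both inputs are assumed.

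| Sessions per week | 20 min | 40 min | 60 min |
|---|---|---|---|
| 1 | 2.9 | 5.7 | 8.6 |
| 2 | 5.7 | 11.4 | 17.1 |
| 3 | 8.6 | 17.1 | 25.7 |

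The sign is positive for the change if only the follow-up week overlaps and negative if only the baseline week does. This assumes that sessions do not displace other activity.

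**3. What could it do to the test?** Inputs from the plan: n = 100 (the recruitment target under Sample size, all assumed to give pairs) and two-sided alpha 0.05. Assumed: 3 × 40 minutes a week in overlapping patients, so 120/7 = 17.1 minutes a day; overlap in the follow-up week only; no true change outside sessions; SD of change 30 or 60 minutes a day. Mean shift = 17.1 × f; noncentrality = shift / (SD/√100).

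| f | Mean shift (min/day) | Rejection probability, SD 30 | Rejection probability, SD 60 |
|---|---|---|---|
| 0 | 0 | 5% | 5% |
| 25% | 4.3 | 29% | 11% |
| 50% | 8.6 | 81% | 29% |
| 100% | 17.1 | about 100% | 81% |

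This is a paired t-test with a common mean shift. The named outcome is a median change and the plan also allows a Wilcoxon test, so the table illustrates sensitivity and does not forecast the study's error rate.

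**4. Can the session count identify overlap?** A count of zero rules it out. Any other count does not settle it: 20 sessions may have been completed by week 10, with no follow-up overlap, while a slow attender with 6 may still be going. At an assumed 2 to 3 sessions a week, the 13th session falls at 13/3 = 4.3 to 13/2 = 6.5 weeks, well before week 13, while continuous attendance to week 13 gives 26 to 39 sessions. At one session a week the 13th falls at week 13 itself, so the link could be closer there. The documents do not say which pattern applies.

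**The case against.** The strongest reply is that no sentence in the documents places a session inside either monitor week. The baseline is meant to come before rehabilitation and the follow-up after it, at least three months from the start on the armband wording. Patients who have finished by then, or who never started, have no follow-up overlap. This stands. A reader might infer that supervised exercise is being counted as daily activity; the documents support only that it may be.

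A reader might also infer that a late start alone creates overlap. That holds only if the months run from enrolment. On the armband wording, a late start moves the follow-up by the same amount.

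It can also be said that exercise in a session is real activity. The documents speak of decreased or measured physical activity and never restrict it to time outside sessions. This stands too: the total is a legitimate quantity, and replacing it would be a choice of estimand that the documents do not dictate. It does not remove the need to tell the two components apart.

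Finally, this is a pilot, activity is one of five characteristics, and a median is less sensitive to a few large shifts. These points lower the priority. They do not close the gap, because modest shifts in a sizeable share of patients move a median as well.

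**Conclusion.** The point holds as a gap in prevention and detection. The plan does not keep either recording clear of sessions and collects nothing that would reveal overlap in a patient with a non-zero session count. The bias in the Aim 1 activity change could run either way, and its extent in the cohort is unknown. In an overlapping patient it is about 3 to 26 minutes a day, on assumed values of 1 to 3 sessions a week and 20 to 60 active minutes each. The rejection probabilities rest on further assumptions about the overlapping share and the SD of change.

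One stronger reading should be set aside. The Analysis plan says "Subgroup analysis will be performed for frail patients and those completing > 6 and > 12 pulmonary rehabilitation sessions", and a reader might infer that the session-count subgroups are the most distorted. That is possible, but a high total does not show attendance during the follow-up week, so bias in those subgroups is not shown.

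The change is a cheap improvement, worth making because the pilot is intended as preliminary data for a larger application.

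**What to change.** 1. Put a short card in the return envelope already supplied, on which the patient records the date, start and stop of any rehabilitation session during each monitor week.
2. Schedule the baseline week to end before the first session where possible, without delaying rehabilitation.
3. State in the Analysis plan that the activity change will be reported both in total and with session time removed at both visits, so that a change outside sessions can be distinguished from the sessions themselves. Neither version needs to be made the sole main outcome.
4. Reconcile the two statements of follow-up timing, including what applies to a patient who does not start rehabilitation.

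The cost is a small diary burden and a few lines of protocol and analysis text. Overlapping weeks will have fewer usable hours; if whole session days were dropped instead, three sessions a week on separate days would leave 4 of 7 days. If patients rest around their sessions, the version with session time removed may understate their activity, which is a reason to show both.

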Effective strategies to improve frailty are unknown. Although patients with moderate to severe lung disease are commonly referred to pulmonary rehabilitation, it is unknown if pulmonary rehabilitation improves frailty or frailty characteristics. The main goal of pulmonary rehabilitation is to improve quality of life in patients with chronic lung disease. Although patients may increase their exercise capacity in pulmonary rehabilitation, this candidate’s preliminary data suggests that frailty persists despite pulmonary rehabilitation in some patients. Certain patient factors have been shown to be associated with successful pulmonary rehabilitation.(14) It is unknown if there are patient factors that contribute to frailty improvement following enrollment in pulmonary rehabilitation. Further study examining the benefits and limitations of pulmonary rehabilitation at effectively addressing frailty and frailty characteristics is essential to improving patient outcomes in chronic lung disease.

The long-term goal for this application is to determine effective interventions to improve frailty in patients with moderate to severe lung disease. The overall objective of the proposed research is to determine if pulmonary rehabilitation improves frailty characteristics in patients with moderate to severe lung disease. Our central hypothesis is that the current model of pulmonary rehabilitation does not optimally address frailty characteristics.

Specific Aim #1 To determine the effectiveness of pulmonary rehabilitation at improving frailty characteristics of slowness (measured gait speed), weakness (grip strength), measured activity, self-reported exhaustion, and wasting (body mass index) in a cohort of patients with moderate to severe pulmonary disease.

Specific Aim #2 To determine if patient characteristics (such as demographics, affect, and uncertainty) are associated with improvement in frailty following pulmonary rehabilitation.

The candidate is uniquely poised to perform this research. She has put together an outstanding team of experts to support her including mentorship expertise in body composition, pulmonary rehabilitation, and frailty, and support from the personnel in the Mayo Clinic Pulmonary Rehabilitation Unit. Importantly, the candidate will have access to a large pulmonary tertiary referral center population and pulmonary rehabilitation facility.

Background and significance

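### The >6 and >12 session subgroups rest on an unverified patient-reported session count, although in-house attendance could be added to the planned record abstraction

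*Combined protocol and SAP*

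**What the plan says.** All references are to the combined protocol and SAP.

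- **Source of the count** (Specific Aim #1, Methods): "Patients will also be asked to specify the number of completed pulmonary rehabilitation sessions". This follows directly after the repeat testing at three to six months, so I read the question as being asked around that visit. No other source is named.
- **Medical record abstraction** (same section): "Patient demographics, pulmonary diagnoses, weight, height, and pulmonary function tests will be recorded". Sessions attended is not in the list.
- **Use of the count** (Analysis plan): "Subgroup analysis will be performed for frail patients and those completing > 6 and > 12 pulmonary rehabilitation sessions". The test named for the pre/post comparison is a signed-rank or paired t-test.
- **Quality assurance**: the regular audit is of the abstraction spreadsheet. Nothing describes checking a patient's stated session count.
- **Who is enrolled** (Specific Aim #1, Participants and Criteria): "Patients who either are referred to enroll in pulmonary rehabilitation at Mayo Clinic in Rochester or who are referred for nursing education" are approached. Entry is therefore by referral, not by attendance.
- **In-house programme**: the Sample size paragraph puts in-house participants at about 150 a year. The Introduction mentions "support from the personnel in the Mayo Clinic Pulmonary Rehabilitation Unit" among the study's resources.

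**The concern.** Patients enter on referral and there is no control arm, so the session count is the only recorded measure of how much rehabilitation anyone received. It rests on a single answer given months after baseline, while grip strength and gait speed are each averaged over three trials and activity is recorded by a monitor.

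Two things can go wrong near a fixed cut-off. Ordinary errors in the stated count move some patients with few sessions into the >6 or >12 group, which pulls the group's mean change toward that of low attenders. Separately, patients who feel they have improved might state a higher count, which would raise the apparent change in those groups even if attendance had no effect. The documents offer no evidence on whether this happens, so I treat it as a possibility only.

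At stake is the reading of the session subgroups, the one place where the plan looks at patients who actually completed a meaningful amount of rehabilitation.

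**Working it through.** The plan gives no figure for the accuracy of the count, so there is nothing to reproduce. The accuracies, subgroup shares and recall errors below are assumptions.

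**1. The quantity the plan estimates.** The planned estimate is the mean pre/post change among patients reported above a cut-off. Let A be the true mean change above the cut-off, B the true mean change at or below it, and PPV the share of those reported above who truly are above. If errors are unrelated to outcome:

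expected estimate = PPV × A + (1 − PPV) × B = A − (1 − PPV) × (A − B)

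The dilution is therefore (1 − PPV) of the true difference A − B.

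**2. PPV from assumed accuracy.** With p the true share above the cut-off:

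PPV = sens × p / [sens × p + (1 − spec) × (1 − p)]

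| p | sens/spec | PPV | Dilution, as % of A − B |
|---|---|---|---|
| 0.5 | 0.90/0.90 | 0.45/(0.45 + 0.05) = 0.900 | 10% |
| 0.5 | 0.80/0.80 | 0.40/(0.40 + 0.10) = 0.800 | 20% |
| 0.3 | 0.90/0.90 | 0.27/(0.27 + 0.07) = 0.794 | 21% |
| 0.3 | 0.80/0.80 | 0.24/(0.24 + 0.14) = 0.632 | 37% |
| 0.7 | 0.90/0.90 | 0.63/(0.63 + 0.03) = 0.955 | 5% |
| 0.7 | 0.80/0.80 | 0.56/(0.56 + 0.06) = 0.903 | 10% |

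For example, if A − B were 3.6 in grip strength (assumed), dilution at p = 0.5 would be 0.36 or 0.72.

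**3. Starting from count error instead.** Take true counts uniform on 0 to 24, so p = 18/25 = 0.72 for >6 and 12/25 = 0.48 for >12. Simulated sensitivity and specificity go into the same formula.

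| Error in stated count | Cut-off | sens / spec | 1 − PPV |
|---|---|---|---|
| SD 1, no bias | >6 | 0.979 / 0.945 | 2% |
| SD 1, no bias | >12 | 0.969 / 0.970 | 3% |
| SD 2, no bias | >6 | 0.956 / 0.888 | 4% |
| SD 2, no bias | >12 | 0.935 / 0.939 | 7% |
| SD 3, no bias | >6 | 0.934 / 0.833 | 7% |
| SD 3, no bias | >12 | 0.901 / 0.908 | 10% |
| SD 2, over-report by 2 | >6 | 0.991 / 0.695 | 11% |
| SD 2, over-report by 2 | >12 | 0.986 / 0.834 | 15% |

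Worked line (SD 2, no bias, >6): 0.956 × 0.72 = 0.688; (1 − 0.888) × 0.28 = 0.031; 1 − PPV = 0.031/0.719 = 4%.

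**4. Reporting related to outcome.** Suppose sessions have no effect, mean change is zero with SD 6.3 (the plan's grip SD, borrowed as the SD of change), and patients with above-average change over-report by 2 sessions (SD 2). Simulation gives a spurious difference between reported groups of about 1.1 at >6 and 0.8 at >12. Because overall mean change is zero, the bias in the reported-above group is that difference times the share reported at or below the cut-off. Over-reporting pushes that share below its true values of 7/25 = 0.28 and 13/25 = 0.52, so the bias is at most about 0.28 × 1.1 = 0.31 and 0.52 × 0.8 = 0.42. A larger sample would not remove it.

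**The case against.** The strongest reply is that the plan contains no dose comparison. That is right. A reader might infer from the two cut-offs that attenders are to be tested against non-attenders, or a dose-response examined. The documents specify paired pre/post tests and subgroups of "those completing > 6 and > 12 pulmonary rehabilitation sessions", with no test across a cut-off. Losses of 20% and 40% at 90/90 and 80/80 apply to a between-group contrast with equal groups (PPV + NPV − 1 = 0.8 and 0.6). For the planned within-group estimate they halve to 10% and 20%.

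A reader might also divide about 150 in-house participants by the 400 to 450 obtained by adding the 250 to 300 education referrals, and conclude that about a third of counts could be verified. The documents do not support this. One figure counts participants and the other referrals, the two may overlap, and the mix in a convenience sample of at least 100 is not given. Where education-referred patients attend is not stated either.

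Three further points stand in part:

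- No section says that session-level attendance is held in the in-house record. The in-house programme and the existing abstraction make it plausible, but it remains an assumption.
- The text does not say the answer is unaided recall, nor does it rule out other sources. What can be said is that no other source or check is described.
- A single source for all patients has merit. Mixing records and self-report lets measurement error differ by programme. This argues for a source flag and a sensitivity analysis, not for leaving the count unchecked.

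**Conclusion.** The point holds as a modest, low-cost improvement. Both session subgroups depend on a patient-stated count that the plan neither abstracts nor checks. The dilution of their pre/post change is about 10% or 20% of the true above-versus-below difference at assumed accuracies of 90/90 or 80/80 with equal groups. It is roughly 5% to 37% if the true share above the cut-off lies between 30% and 70%, and 2% to 10% under random count errors of SD 1 to 3 sessions with the assumed uniform counts. Bias from reporting tied to perceived benefit is possible but undocumented. The documents fix none of these accuracies.

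The reach is narrow. Neither the overall pre/post comparison nor the Aim 2 outcomes as listed use the count, and the study describes itself as a pilot. Nothing here calls the main result into question.

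**What to change.** 1. Add sessions attended to the medical record abstraction for patients in the in-house programme, after confirming that attendance is recorded there, and use that count to form the >6 and >12 subgroups.
2. Still ask every patient for the count, and use the answer for those whose attendance cannot be abstracted.
3. Flag the source of each count, and report agreement wherever both sources exist. This indicates how far self-report can be relied on for the remaining patients.
4. Repeat the subgroup results with self-report for all patients as a sensitivity analysis.

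The cost is one field in an abstraction that is already planned and audited, plus one extra table. The downside is two data sources whose error may differ by programme. How many counts can be verified will be known only once enrolment shows where patients attend.
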